#### 4.4.5 Vital Sign Measurements

The vital sign measurement panel will include blood pressure, respiratory rate, heart rate, and temperature. Observed results at each visit will be presented. The vital sign data at baseline and change from baseline for each scheduled post dose visit will be summarized with descriptive statistics by actual treatment group. Change from baseline will only be calculated for subjects having non-missing baseline and post-baseline measurements.

All vital sign measurements will be presented in a by subject listing.

#### **4.4.6 Bleeding Events**

A summary table for the number and percent of unique subjects with at least one major bleeding event during the 28 day study period, along with 95% exact confidence interval of the bleeding rate for each treatment and the exact risk difference between two treatment groups in bleeding rates, will be presented using the safety population. The count and percent of unique subjects experiencing at least one bleeding event by Study Days 3, 7, and 14 will be presented in the same table, but confidence intervals and risk difference will not be provided. Subjects will be counted as having experienced a major bleeding event from the earliest recorded event through all subsequent time points.

A bleeding event is considered on-treatment provided it occurs within five days past last dose. An after-treatment event is any event with an onset date of six or more days past last dose date. A summary of on-treatment and after-treatment major bleeding events will be presented by treatment arm and overall. If a subject experiences both an on-treatment and after-treatment event the subject will be counted in both summaries; that is, on-treatment and after-treatment event summaries may not be disjointed.

A similar summary will be presented for serious major bleeding events as well.

Additionally, the differences in major bleeding event rates will be presented by country, new infections, concomitant heparin use through day 7, renal function through day 7, baseline RRT, and on treatment RRT

Adverse events and serious adverse events identified as bleeding events will be summarized by primary system organ class (SOC) and preferred term (PT) for on treatment and off treatment separately.

All bleeding event data will be presented in a data listing.

#### **4.4.7 Pregnancies**

A by-subject listing will present pregnancy results, including serum or urine hCG, for subjects who are pregnant based in the FAS population.

#### **4.5 Pharmacokinetic Analyses**

Plasma concentration data will be summarized in tables and figures by actual treatment group by sampling timepoints (pre and post dose sampled displayed separately) as outlined in [Table 1](#). The results will also be presented in a listing.

Plasma concentration data will also be presented by treatment group in a by subject listing.

## 5 Interim Analysis

Only subjects randomized prior to the DMC database lock date (i.e., 8 weeks prior to the DMC meeting) will be considered evaluable for the primary efficacy and futility analyses at each of the interim analyses.

Early termination of the study for efficacy will not be actively pursued. However, should the primary efficacy results surpass an O'Brien-Fleming type boundary using a two-sided alpha level of 0.001 and the DMC believes the study results are extremely robust and so positive it is unethical to continue the study they may recommend termination of the study for efficacy. The alpha level for this O'Brien-Fleming boundary has been selected to result in a negligible impact on both decision rules outlined in [Section 2.2](#). The impact on the final alpha level at the 0.1% level is very small but is non-zero. The alpha spent at the interim analysis is approximately 0.00005. Due to the small size of this alpha spend no adjustment to final alpha level will be made.

Early termination for futility will be assessed using a Mantel-Haenszel difference of proportions with pooled site as a stratification factor. If the lower bound of the confidence interval around the difference of proportions ( $M_{ART} - M_{PIb}$ ) exceeds -0.06 then this will be considered sufficient evidence to rule out clinically meaningful benefit. The alpha spending rule and corresponding confidence interval that will be produced for each DMC plus the final analysis will use a Lan-DeMets approach. [Table 3](#) is an example of how the alpha spending would look if the interims occurred at 150, 300, 450 and 600 subjects as planned.

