2.7.2.3 Discontinuation due to lost to follow up

Subjects who have not withdrawn consent, but have not returned for follow-up visits and no contact can be made to determine their status will be designated "Lost to Follow-up". Site personnel will designate a subject as Lost to Follow-up for the primary endpoint at Day 28 only after the subject or subject's representative has not responded to two documented attempts at telephone contact and a registered letter sent to the subject's last known mailing address. The Lost to Follow Up date will be recorded as the last date of contact with the subject. For all subjects who are lost to follow-up the investigator will report if, in the investigator's judgment, the subject was improving and likely to be alive on Day 28.

For subjects who have not withdrawn consent, site personnel are asked to make every attempt to collect long term survival status at the 3 month, 6 month and 12 month time points. Subjects are to be classified with a final status of "Lost to Follow Up" only if they are unable to be contacted at the 12 month survival status time point.

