## **2 Investigational Plan**

### **2.1 Study Design**

This is a randomized, double-blind, placebo-controlled, multi-center, parallel-group study of ART-123 in subjects with coagulopathy due to severe sepsis and a concurrent diagnosis of shock and/or respiratory dysfunction that requires mechanical ventilation for hypoxemia.

Following screening, subjects who meet all inclusion criteria and none of the exclusion criteria will be randomly assigned, in a 1 to 1 ratio, to receive ART-123 in a dose of 0.06 mg/kg/day up to a maximum dose of 6 mg/day or a matching placebo for 6 consecutive days. The study period will be 28 days from the time of the start of treatment. Long term follow-up to determine mortality status will be conducted at 3, 6 and 12 months after the start of treatment.

The primary endpoint is all cause mortality status 28 days after the start of treatment (mortality day 28). Blood samples for assessing coagulation and inflammation parameters, ART-123 concentration, organ dysfunction, and safety laboratory tests will be obtained between baseline and the day 28 assessment. Safety-related assessments will include reports of adverse events, major bleeding events, ECGs and clinical laboratory test results.

The study will utilize an independent Data Monitoring Committee (DMC). The DMC's primary responsibility will be to review safety findings. There are also provisions for them to perform interim analyses for early stopping due to efficacy as well as futility.

The clinical database will be locked and analyses performed after the last subject has completed 28 days on study. At that time, the long-term mortality data will not be known for all subjects. These long-term mortality data will be collected and analyzed after the primary database lock and analyses.

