### 3.4 Handling of Missing Data

For testing of the primary endpoint, Day 28 all-cause mortality status, subjects with unknown mortality status will be imputed. Investigators will be asked to assess whether at the last point

they had contact with the subject, the subject's health was such that it was unlikely they would be alive at day 28. If so, it will be assumed the subject was dead at day 28. Otherwise the subject will be classified as alive for the primary analysis. This imputation will only be used for the day 28 mortality status analysis.

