### 3.6 Statistical Assessment of the Trial Objectives

#### 3.6.1 Mortality Status

The primary hypothesis for this study is as follows:

$$H_o : M_{ART} \geq M_{plb}$$
$$H_a : M_{ART} < M_{plb}$$

Where in  $M_{ART}$  and  $M_{plb}$  are the mortality rates 28 days after treatment for the ART-123 and Placebo treatment arms. The primary analysis will test these hypotheses on the Full Analysis Set. The statistical test that will be used is a Cochran-Mantel-Haenszel test (LaVange, Durham and Koch, 2005) controlling for pooled site (see section 3.5). Subjects with missing/unknown mortality status at Day 28 will have their mortality status imputed as outlined in Section 3.4.

P-values will be reported as two sided p-values and compared to the two sided decision rules outlined in Section 2.2. Statistically significant positive results will be based upon achieving a reduction in mortality.

Mortality status 28 days after the start of treatment will be determined by evaluating the date of death if a subject died, or the last known contact date if the subject is not known to have died. If the date of death is 28 days or less from the start of treatment (Date of death – Date of first

treatment  $\leq 28$ ) the subject will be classified as dead at 28 after the start of treatment (Mortality Day 28). If the Date of death is more than 28 days after the start of treatment the subject is classified as alive at Mortality Day 28. Subjects without evidence of death will be classified as alive if their last contact date is 28 or more days after the start of treatment (Last Contact date – Date of first treatment  $\geq 28$ ). If the last contact date with a subject is less than 28 days after the first treatment the mortality status for the subject will be considered unknown and imputed as outlined in see [Section 3.4](#).

Summary measurements of survival status will include the following:

- a) Mortality status (dead, alive, unknown) at Study Day 3, 7 and 14
- b) Kaplan Meier plots of time until death
- c) Kaplan Meier estimate of mortality rates at Mortality Day 28

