### 3.8 Interim Analysis

This study will include un-blinded interim analysis (IA) performed by a Data Monitoring Committee. There will be 4 IAs planned to occur when 150, 300, 450 and 600 subjects are evaluable for the 28 day all-cause mortality endpoint.

The DMC may recommend termination or modification of the study based upon a review of the totality of the data. Early termination of the study for efficacy will not be actively pursued however guidelines regarding this are provided in [Section 5](#).

Analyses to rule out clinically meaningful benefit will also be performed. The goal of these analyses is to stop the study if sufficient evidence exists that there is not a clinically meaningful treatment benefit. The futility analyses will be conducted with the use of a lower O'Brien-Fleming-type boundary. This boundary will be constructed using a one-sided alpha level of 0.20 and will test the hypothesis given below:

$$H_o : M_{ART} < M_{plb} - 6\%$$
$$H_a : M_{ART} \geq M_{plb} - 6\%$$

Confidence intervals will be used to evaluate these hypotheses as outlined in [Section 5](#).

Termination or modification of the study due to safety concerns will not be limited to a fixed set of analyses.

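### SAP section 5 sets no minimum follow-up for subjects counted at the interim looks, which conflicts with section 3.8; the numerical effect is small

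*SAP*

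**What the plan says.** Five places in the plan bear on this.

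- **SAP 5 (Interim Analysis)** limits the set used for the interim efficacy and futility analyses: "Only subjects randomized prior to the DMC database lock date (i.e., 8 weeks prior to the DMC meeting) will be considered evaluable". It states no minimum time since first dose.
- **SAP 3.8** times the four looks for "when 150, 300, 450 and 600 subjects are evaluable for the 28 day all-cause mortality endpoint".
- **SAP 3.6.1** covers subjects with no evidence of death, and its condition for an unknown status reads: "last contact date with a subject is less than 28 days after the first treatment the mortality status for the subject will be considered unknown". Section 3.4 then governs how that status is filled in.
- **SAP 3.4** asks whether the investigator, at last contact, thought survival to Day 28 unlikely: "If so, it will be assumed the subject was dead at day 28. Otherwise the subject will be classified as alive for the primary analysis".
- **SAP 2.1**, for the final analysis, does set a maturity condition: "The clinical database will be locked and analyses performed after the last subject has completed 28 days on study".

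Protocol 2.7.2.3 describes the investigator's judgement about Day 28 for one group: "For all subjects who are lost to follow-up the investigator will report if" the subject was improving and likely to be alive. It does not ask for that judgement on subjects who are simply still being followed. SAP 3.6.5 says that extra sensitivity analyses for the interims are set out in 3.8, but 3.8 contains none.

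**The concern.** A subject randomised shortly before the lock satisfies the one condition in section 5 but cannot yet have a 28-day outcome. Unless data are collected after the lock, such a subject is either a known early death or unknown, and most unknowns would become alive. If ART-123 works, this removes not-yet-observed deaths from both arms and pulls the difference towards zero. The futility rule stops the trial when the lower confidence limit for ART-123 minus placebo lies above -6 points, so shrinkage favours stopping an effective drug. It also makes the efficacy boundary harder to reach. In addition, immature subjects would count towards the 150/300/450/600 triggers, so the information behind the SAP Table 3 bounds would be overstated.

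**Working it through.** **Inputs from the documents.** 800 subjects, 1:1, 24% vs 16%, two-sided 5% (SAP 2.3). Looks at 150, 300, 450 and 600 (SAP 3.8). Futility margin -0.06 and one-sided 0.20 O'Brien-Fleming-type spending (SAP 3.8 and 5). Enrolment estimated from 3Q 2012 to 3Q 2018 (Protocol Synopsis).

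**Assumptions.** Accrual is even, and the pending number is varied up to about four times the average. Entry is uniform within the last 28 days. Deaths are uniform over 28 days, with a front-loaded alternative. Data are frozen at the lock, and pending subjects without a recorded death count as alive.

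**1. The plan's own figures.**
- Power: null SE = √(0.20 × 0.80 × 2/400) = 0.0283; alternative SE = √((0.24 × 0.76 + 0.16 × 0.84)/400) = 0.0281. Then (0.08 - 1.96 × 0.0283)/0.0281 ≈ 0.87, giving 80.9% against the stated approximately 80%.
- Table 3: cumulative spend = 2[1 - Φ(z₀.₉₀/√t)] at t = 150/800, 300/800, 450/800, 600/800 and 1 gives 0.0031, 0.0364, 0.0875, 0.1389 and 0.200. These match within rounding, as do the nominal levels.
- The stated 0.6% chance of a futility stop under 16% vs 24% did not reproduce in the unstratified simulation of step 4. That is a separate matter; only changes from the simulation's own baseline are used here.

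**2. How many subjects are pending.** Six years is 6 × 365.25/28 = 78.3 periods of 28 days, and 800/78.3 = 10.2 subjects per period.

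| Pending at lock | Look 1 (150) | Look 2 (300) | Look 3 (450) | Look 4 (600) |
|---|---|---|---|---|
| 10.2 | 6.8% | 3.4% | 2.3% | 1.7% |
| 40 | 27% | 13% | 9% | 7% |

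**3. Shrinkage of the difference.** With pending share f, and a fraction q of pending subjects' deaths not yet observed, the expected difference is -8 × (1 - f·q) points. Uniform deaths give q = 1/2. At look 1:
- 10 pending: -8 × (1 - 0.0667/2) = -7.73
- 20 pending: -8 × (1 - 0.1333/2) = -7.47
- 40 pending: -8 × (1 - 0.2667/2) = -6.93

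If cumulative mortality follows the square root of time, q = 1/3 and 40 pending gives -8 × (1 - 0.2667/3) = -7.29. At look 4 with 10 pending and uniform deaths, the shrinkage is 8 × (10/600)/2 = 0.07 points.

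**4. Chance of a wrong futility stop.** 40,000 simulated trials at 24% vs 16%, unstratified difference, Table 3 levels, cumulative over four looks, uniform deaths:

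| Pending per look | Table 3 as two-sided intervals | Table 3 as one-sided bounds |
|---|---|---|
| 0 | 2.3% | 5.0% |
| 10 | 2.4% | 5.2% |
| 20 | 2.6% | 5.5% |
| 40 | 2.9% | 6.0% |

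The simulation standard error of each figure is about 0.1 point, for example √(0.05 × 0.95/40,000) = 0.0011.

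**5. Why the result is so flat.** The bias is largest at look 1, where the bound is hardest to cross. With 75 per arm the SE is √((0.24 × 0.76 + 0.16 × 0.84)/75) = 0.065. Stopping then needs an observed difference of about -0.06 + 2.75 × 0.065 = +0.12 (one-sided) or -0.06 + 2.97 × 0.065 = +0.13 (two-sided). That is ART-123 mortality 12 to 13 points worse than placebo.

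**6. Information.** If 10 of 150 subjects carried no information, the look-1 fraction would be 140/800 = 0.175 rather than 0.1875. The spend due would be 2[1 - Φ(1.2816/√0.175)] = 0.0022 rather than 0.0031.

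**The case against.** The strongest reply is that section 5 states a restriction, not a full definition. It excludes subjects randomised after the lock; it does not say that everyone randomised before it is evaluable. Randomisation alone cannot be enough in any case, because the primary analysis uses the Full Analysis Set, which requires a dose. On this view 3.8 supplies the missing condition by requiring evaluability for a 28-day endpoint.

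The eight weeks point the same way. First dose is due within 4 hours of randomisation (Protocol 5.4), so anyone randomised before the lock is past Day 28 with about 56 - 28 = 28 days to spare before the meeting. The sentence may be meant as a randomisation cut-off with time left for outcomes to mature. The DMC Charter, which is not among these documents, may also settle the matter.

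Much of this stands. A reader might infer that immature subjects certainly enter the interim tests and are all set to alive. The documents do not support that. Deaths before the lock count as deaths, an adverse investigator assessment gives dead, and applying 3.4 to pending subjects is an inference that no section states.

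What does not stand is that the text is adequate. The benign reading needs mortality status to be updated after something called a database lock, and neither document provides for that. If section 5 is only a restriction, the SAP has no operational definition of interim evaluability. By contrast, it states the 28-day condition expressly for the final lock.

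**Conclusion.** The point holds as a minor defect of definition. Section 5 admits subjects by randomisation date with no follow-up requirement, 3.8 implies a completed 28-day endpoint, and the SAP does not say how subjects pending at the lock are handled.

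On the literal reading the bias runs towards no difference. At the planned average accrual it is roughly a quarter of a point at look 1 and under 0.1 point at look 4. The rise in wrong futility stops is then about 0.2 to 0.3 points, which is negligible. At four times that accrual it is about 0.6 to 1.1 points. Front-loaded deaths make all of these smaller, and on the benign reading they vanish.

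A reader might infer that the trial runs a material risk of stopping wrongly for futility because of this; the figures do not support that. The final analysis is untouched. The sizes rest on assumed accrual and death timing and on an unstratified simulation.

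**What to change.** Replace the evaluability sentence in SAP 5 with a rule along these lines: at each interim, evaluable subjects are those in the Full Analysis Set whose first dose was at least 28 days before the interim mortality data cut-off. State that cut-off date separately from the randomisation cut-off, so that the rule also works if status is meant to be updated before the meeting. Count the 150/300/450/600 triggers and the information fraction on this set.

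Add that the 3.4 imputation is not applied to subjects whose follow-up is only pending; it remains for mature subjects whose status is genuinely unknown. Define the set by first-dose date rather than by known status. Otherwise early deaths among recent subjects would be counted while their surviving contemporaries were left out.

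The cost is a sentence or two in the SAP. About 10 recent subjects wait for the next look, or the cut-off moves by four weeks.

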10.3.2 Stopping for Efficacy

Early termination of the study for efficacy will not be actively pursued unless it would be unethical to continue the study based upon the magnitude of benefit observed. In this situation should the primary efficacy results surpass an O'Brien-Fleming type boundary with Lan-DeMets implementation based upon a two-sided alpha level of 0.001 and the DMC believes the study results are extremely robust and so positive it is unethical to continue the study they may recommend termination for efficacy.

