10.3.3 Stopping Due to Lack of Clinically Meaningful Benefit/Futility

An analysis to rule out clinically meaningful benefit will also be performed. The goal of these analyses is to stop the study if sufficient evidence exists that there is not a clinically meaningful treatment benefit. The futility analyses will be conducted with the use of a lower O'Brien-Fleming type boundary. This boundary will be constructed using a one-sided alpha level of 0.20 and the hypothesis: the 28-day mortality rate on ART-123 is reduced by 6%. Should interim analyses be performed after the 600 subjects time-point (75% information) the DMC will interpret the results of the futility calculations in context of the remaining enrollment.

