### **2.3 Sample Size**

The primary analysis for this study will be based on a stratified Cochran-Mantel-Haenszel test. For sample size and power calculations a Chi-squared test has been used. A sample size of 800 subjects provides approximately 80% power if the following assumptions are made:

1. 5% two-sided alpha level
2. 8% treatment effect (24% placebo mortality rate vs. 16% ART-123 mortality rate).
3. 1 to 1 randomization

The assumed treatment effect and mortality rates are based upon post-hoc results from study 2-001 and assume the day 28 mortality status will be known for all subjects.

A sample size of 800 subjects and these assumptions also provides 32% power for a 0.1% two-sided  $\alpha$  level. If the true treatment effect is 12% (24% vs. 12%), a sample size of 800 provides greater than 80% power when a 0.1% alpha level is used.

In this 800 subject study, an observed treatment benefit of approximately 6% is expected to result in a p-value less than 5% and a difference of approximately 9% is expected to result in a p-value less than 0.1%.

The sample size and power calculations were performed with Pass 2007.

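### The interim efficacy alpha spend of 0.00005 carries no side and appears to be a one-sided figure set against a two-sided 0.001 level; the two-sided spend is about 0.00012

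*SAP*

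**What the plan says.** SAP section 5 lets the DMC recommend stopping for efficacy "should the primary efficacy results surpass an O'Brien-Fleming type boundary using a two-sided alpha level of 0.001", if it also judges the results so strong that continuing would be unethical. Protocol section 10.3.2 gives the same rule and names the spending approach: an "O'Brien-Fleming type boundary with Lan-DeMets implementation based upon a two-sided alpha level of 0.001". On timing, SAP section 3.8 says: "There will be 4 IAs planned to occur when 150, 300, 450 and 600 subjects are evaluable".

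SAP section 5 then describes the impact on the 0.1% level as very small though not zero, and quantifies it: "The alpha spent at the interim analysis is approximately 0.00005". The conclusion drawn is: "Due to the small size of this alpha spend no adjustment to final alpha level will be made".

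The 0.1% level is the upper category of the decision guideline in SAP section 2.2 and protocol section 10.1.1. A two-sided p-value below 0.001, if supporting analyses corroborate it, is taken to remove the need for a second confirmatory study. SAP section 3.6.1 says that p-values are two-sided and are compared with two-sided decision rules.

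**The concern.** The 0.00005 has no side attached. Everything around it is two-sided: the boundary's alpha, the 0.1% rule and the reported p-values. A reader will therefore set 0.00005 against 0.001 and conclude that the interim looks use 5% of the error budget. If the boundary really spends more than twice that on the two-sided scale, the only quantitative reason given for leaving the final level alone is understated.

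The 5% rule is not at stake, because a boundary this extreme barely touches it. What is at stake is the error rate of the 0.1% rule, which carries the claim that one trial is enough. A number supporting that claim should be on the same scale as the rule, and should be reproducible from the plan.

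**Working it through.** **Inputs**
- Boundary: O'Brien-Fleming type, Lan-DeMets, two-sided 0.001, hence 0.0005 per side (SAP section 5; protocol section 10.3.2).
- Looks: 150, 300, 450 and 600 evaluable subjects (SAP section 3.8).
- Maximum: 800 subjects (SAP section 2.3). Information fractions t are therefore 0.1875, 0.375, 0.5625, 0.75 and 1. Protocol section 10.3.3 also puts 600 subjects at 75%.

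**Formula.** The one-sided cumulative spend is f(t) = 2 × [1 − Φ(z / √t)], where z is the upper a/2 normal quantile and a is the one-sided alpha. The symmetric two-sided spend is 2 × f(t).

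**Check against the plan's own figures.** With a = 0.20 (the futility boundary), z = 1.2816:

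| Subjects | Computed f(t) | SAP Table 3, cumulative |
|---|---|---|
| 150 | 0.0031 | 0.003 |
| 300 | 0.0364 | 0.036 |
| 450 | 0.0875 | 0.087 |
| 600 | 0.1389 | 0.139 |
| 800 | 0.2000 | 0.200 |

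The function and the information fractions therefore match those behind Table 3 (the 450-subject value is 0.08749997 before rounding).

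**Efficacy boundary.** With a = 0.0005, z = 3.4808:

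| Subjects | z / √t | One-sided cumulative | Two-sided cumulative |
|---|---|---|---|
| 150 | 8.038 | 9.1e-16 | 1.8e-15 |
| 300 | 5.684 | 1.3e-8 | 2.6e-8 |
| 450 | 4.641 | 3.5e-6 | 6.9e-6 |
| 600 | 4.019 | 0.0000584 | 0.000117 |

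The increment at the fourth look alone is 0.0000549 one-sided and 0.000110 two-sided.

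**Comparison with the stated 0.00005**
- Against the two-sided cumulative spend: 0.00005 / 0.000117 = 43%.
- Against the two-sided fourth-look increment: 0.00005 / 0.000110 = 45%.
- Against the one-sided values of 0.000055 and 0.000058: close.
- Share of budget: 0.000117 / 0.001 = 12% two-sided, and 0.000058 / 0.0005 = 12% one-sided. The 5% comes only from dividing a one-sided spend by a two-sided level.

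**Other versions of the boundary.** The two-sided spend by 600 subjects is 0.000145 if the spending function is evaluated with a = 0.001, 0.000139 for the classical O'Brien-Fleming boundary at the planned looks, and 0.000219 for the classical boundary at equally spaced looks. None is near 0.00005. A two-sided Lan-DeMets spend of 0.00005 would need the last interim at t = 0.68, about 546 subjects.

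**Effect on the final test, by recursive numerical integration**
- Boundary z-values at the four interims: 7.95, 5.56, 4.50 and 3.86.
- Final z that holds two-sided 0.001 overall: 3.30, a nominal two-sided level of 0.00096.
- Final test left at 0.001 (z = 3.29): overall two-sided error 0.001038, an excess of 0.000038. This is less than the 0.000117 spent because most interim crossings would also cross at the end.
- Final test at 0.05: overall two-sided error 0.0500002.

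**The case against.** The strongest reply is that 0.00005 is not wrong, only unlabelled. The hypotheses in SAP section 3.6.1 are directional, a positive result means a reduction in mortality, and an efficacy stop can occur only in that direction. The chance of falsely stopping for benefit is then the one-sided spend, and 0.000055 to 0.000058 is close to the stated figure. This stands as the likeliest explanation. It does not rescue the comparison: a one-sided spend belongs beside 0.0005, where the share is again 12%.

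The second reply is that nothing follows from the correction. The SAP already says that the impact is not zero, and the true excess of 0.000038 is no larger than the number it quotes. The top category also needs corroborating analyses, and stopping needs a DMC judgement, so 0.00104 counts every crossing as a claim and is an upper limit. All of this stands, and it is why the point is minor.

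A reader might infer two stronger things. One is that the stated spend is simply an arithmetic error that more than halves the truth. The documents do not support this, since nearly all of the gap is the factor of two between one side and two. The other is that the SAP departs from the protocol by testing at 0.001 although the Lan-DeMets boundary implies a lower final level. They do not support that either: protocol section 10.3.2 uses the boundary as an early-stopping guideline, and protocol section 10.1.1 sets the final threshold at 0.001, as SAP section 2.2 does.

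**Conclusion.** The point holds as a correction of scale. Next to a two-sided boundary and a two-sided rule, the interim spend should read about 0.00012, not 0.00005, and the looks use about 12% of the 0.001 budget. The figure matters because it is the SAP's stated reason for making no final adjustment on the rule that would waive a second study.

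The practical effect is small. Overall two-sided error at the 0.1% rule is at most about 0.00104, roughly 4% above nominal in relative terms, and the 5% rule is untouched. The SAP's qualitative statement about the impact remains true.

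These results assume a symmetric two-sided Lan-DeMets O'Brien-Fleming boundary, looks at exactly the planned counts out of 800, and every boundary crossing treated as a claim. The one-sided origin of 0.00005 is an inference from the closeness of the numbers; the SAP does not say so.

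**What to change.** In SAP section 5, restate the spend as about 0.00012 two-sided, or label the figure as one-sided (about 0.00006) and compare it with 0.0005.

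For the 0.1% rule, use the boundary's own final nominal level: about 0.00096 at the planned looks, recomputed at the looks that actually occur. If the sponsor prefers to keep 0.001, state the resulting overall two-sided error of about 0.00104, so that the choice rests on the right number.

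The 5% rule, sample size and trial conduct stay as they are. The cost is an edit to two figures and, under the first option, a slightly stricter top-category threshold (z about 3.30 instead of 3.29). Using 0.00096 would also mean aligning the 0.1% wording in protocol section 10.1.1 and SAP section 2.2.
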